1. Incidence of hemodynamic instability, which is defined as a mean arterial pressure (MAP) dropping below 65 mmHg or decreasing by more than 20% from the baseline within 20 minutes after the induction of anesthesia.
2. Intraoperative consumption of vasopressors.
3. Length of postoperative hospital stay, calculated as the time interval between the index surgery and the patient's discharge from the hospital.
4. Rate of ideal postoperative recovery, determined as uneventful discharge within 5 days after surgery (without major complications, classified as \geq III according to the Clavien-Dindo classification, incision infection, and readmission);
5. Proportion of patients with Clavien-Dindo classification Grade IV complications, which is defined as life-threatening complications requiring ICU management, such as single organ dysfunction (including dialysis) or multiorgan dysfunction.

Exploratory outcomes

1. Each individual component of the composite primary endpoint (by organ system and by different Clavien-Dindo classification Grades)

2. 30-day all-cause mortality;
3. Incidence of unplanned ICU admission;
4. Incidence of unplanned reoperation;
5. Incidence of in-hospital complications;
6. Barthel index for activities of daily living (ADL) at 30 days after surgery.

Safety Outcomes

1. Incidence of acute kidney injury diagnosed by KDIGO criteria;³¹
2. Massive intraoperative bleeding (hemorrhage exceeds 1000 ml);
3. Episodes of intraoperative hypotension defined as SBP < 90 mm Hg or drop \geq 30% of baseline lasted for 5 min;
4. Episodes of hypertension defined as SBP > 180 mm Hg or rise \geq 30% of baseline lasted for 5 min;
5. Arrhythmia that consisted of bradycardia (heart rate < 40 beats per minutes), tachycardia (HR > 100bpm) or new onset of arrhythmia that require anti-arrhythmic drugs;
6. Airway hyper-responsiveness defined as a airway peak pressure > 40cm H₂O).

All outcomes will be discussed and evaluated by the endpoint assessment committee and documented as appropriate. All adverse events must be recorded in CRFs and documented. The reporting of SAE follows the

institutional requirement and local regulations.

STATISTICAL ANALYSIS PLAN

Scope of the Analysis plan

This Statistical Analysis Plan (SAP) presents the statistical consideration in design and analyses for COIN trial. The final manuscript will strictly follow this SAP.

Sample Sizes

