In order to detect a 13% absolute reduction (from 33% to 26%) for the primary outcome of postoperative complications of Clavien-Dindo Grade \geq I up to 30 days after surgery (a risk ratio of 0.8), with 90% power and an overall type I error rate of 5%, a total of 2020 patients (1010 per arm) are required, accounting for 10% drop-out rate.

Randomisation procedure

Randomisation will occur after obtaining informed consent from the eligible patients and shortly before the index surgical procedure is due to start (last-minute randomization). Patients will be centrally allocated to treatment arms in a 1:1 ratio by permuted block randomization stratified with participant centers. To enter a patient into the COIN trial, research staff at each participant site will log on to a secure web-based randomization platform of Redcap data

entry system and obtain a unique patient identification number and allocation assignment. This information will be only revealed to the unblinded investigator who prepare the intervention fluids.

Datasets for Analyses

All statistical analyses within this study will be performed following the intention-to-treat principle. This implies that patients will be analysed in accordance with the treatment groups to which they were initially assigned, as depicted in Figure 1. It is expected that there will be either no or very minimal losses to follow-up for primary and secondary outcomes considering the prospective feature. Patients with missing primary outcome data will be excluded from the analysis (complete-case analysis approach). Missing data for baseline covariates to be included in the analysis model will be accounted for using multiple imputation.

Participation of individual patient in the study will be terminated if they (or their trusted person) withdraw consent. However, if the investigator discontinues the patient's participation, either temporarily or permanently, for reasons in the patient's best interest, especially when serious adverse events are suspected to be related to the intervention, the patient will remain in the analysis to uphold the intention-to-treat principle. Their data will continue to be collected until 30 days after surgery, which marks the final follow-up.

Modified Intent-to-Treat (m-ITT) population excludes individuals who had their

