surgical procedures canceled after randomization, patients who withdrew their consent. The as-treated population is defined by the treatment that was actually received during the trial. This takes into account any deviations from the initially assigned treatment regimen, such as crossovers to the other treatments. The Per-Protocol (PP) population consists of all patients who received the assigned treatment without significant deviations from the protocol. Specifically, the analysis will be restricted to those who completed the full-term intervention as it was initially assigned. Participants with treatment interruptions will be excluded from the PP analysis. The exclusion list will be verified by the steering committee prior to lock of the database. Analyses conducted on these dataset will be treated as supplementary analyses.

General analysis Principles

The COIN trial is designed to assess the impact of preoperative colloid infusion on the occurrence of postoperative complications in surgical patients undergoing non-cardiac surgery with general anesthesia. The estimand is the difference in the incidence of postoperative complications as defined by higher than grade I Clavien-Dindo classification at 30 days after surgery between Colloid bolus administration versus crystalloid bolus administration, in patients undergo elective non-cardiac surgery under general anesthesia. The target population is patients experienced surgery procedure. The patients have the planned surgery canceled after randomization will be excluded from the

primary analyses.

In general, categorical variables are to be compared using χ^2 test or Fisher's exact test. Continuous variables will be compared via t-test or Wilcoxon's rank-sum test. Variable normality will be assessed either via the Shapiro-Wilk test or QQ-plots and residual plots. Variable transformation such as natural logarithm or square root will be applied where necessary, or non-parametric methods (such as Wilcoxon rank sum test) shall be applied.

For the analyses of primary, secondary outcomes, and the process measures, the following information will be presented:

- 📅 The number of patients included in each analysis, by treatment arm
- 📅 A summary statistic of the outcome (such as, number (%), mean (sd), media (IQR), etc), by treatment arm
- 📅 The estimated treatment effect
- 📅 A 95% confidence interval for the estimated treatment effect
- 📅 A two-sided P value

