For all analyses, a significance level of 5% will be used. Multiple comparisons will be conducted without Type I error correction and will be interpreted as exploratory.

Data Presentation and Baseline characteristics

Baseline characteristics will be summarized using descriptive statistics for whole patients cohort and for each treatment group by mean and standard

deviation or median and interquartile range for continuous variables, and the number, frequencies, and percent for categorical variables.

Durations According to Dates

For the indexed surgery, the date of randomization or admission to the intensive care unit corresponding to the surgery date will serve as day 1.

Take, for example, the calculation of the postoperative hospital stay (in days).

The formula is: (Discharge date from hospital - Date of index surgery) + 1

Exact dates will be tracked and documented.

Analysis of the primary endpoints

The primary endpoint, incidence of postoperative complications as defined by higher than grade I Clavien-Dindo classification at 30 days after surgery will be analyzed using Chi-squared test as crude analysis. Unadjusted risk ratios with 95% confidence intervals will be estimated by two-by-two table with the use of log-Normal approximation or other approximation/numeric methods as appropriate. The effect size will be expressed as risk differences (95% confidence intervals) will be estimated using Wald's likelihood ratio approximation test or other methods appropriate, with the number needed to treat as the reciprocal of the risk difference, rounded to the nearest integer.

Secondary Analyses of the primary endpoint

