To account for potential confounders, the adjusted analysis of primary endpoint will use a logistic regression model, where the primary endpoint as the dependent variable and independent variables to include study group (colloid fluid bolus group vs crystalloid fluid bolus group), adjusting for the relevant confounders (planned surgical procedure complexity grade, ASA grade, gender, age, baseline hemoglobin, and baseline creatinine, NPO duration, fluid administration within 12 hours prior to surgery). Odds ratios (95% confidence intervals) will be reported; for those ORs may potentially be biased approximation for RRs, estimates will be obtained via either binomial regressions or converted using bootstrap methods. We will also develop a logistic regression model accounting for the above variables plus any baseline characteristics that appear on visual review to be potentially imbalanced between the study groups.

To account for the center effects, we will fit a mix-effect model with the primary outcome as dependent variable, including group assignment as a fixed effect and participant center (stratification variable) as a random effect. Potential confounders that included in the model are the same as the logistic regression model. Alternative method to use if mixed-effect models fail to reach convergence:

- Include participant sites as a fixed-effect instead of random effect.
- Remove the fixed effect for participant sites
- Adjust for age, hemoglobin, creatinine, fasting duration, etc as a single

continuous variable.

- Remove the covariates in prespecified order to see if convergence reached: gender, hemoglobin, creatinine, age, surgical complexity, ASA grade.

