Rate of ideal postoperative recovery within 5 days of surgery will be analysed using a logistic regression model, adjusting for planned surgical procedure complexity grade, ASA grade, gender, age, baseline hemoglobin, and baseline creatinine. Similar will be conducted for as above for cases of computing complexities.

Analyses of exploratory outcomes

Each individual component of the composite primary endpoint (by organ system and by different Clavien-Dindo classification Grades)

This will be analyzed using the same approach as for the analysis of the primary outcome above. Unadjusted Chi - squared test will be used.

Thirty day all-cause mortality

The expected event rate for this endpoint is extremely low. Thus, descriptive statistics will be used. Fisher exact test will be used to compare between group difference.

Incidence of unplanned ICU admission;

This outcome will be compared either using Chi-square test or Fisher exact test as appropriate depending on rate.

Incidence of unplanned reoperation

This outcome will be compared either using Chi-square test or Fisher exact test as appropriate depending on rate.

Incidence of in-hospital complications

This outcome will be compared either using Chi-square test or Fisher exact test as appropriate depending on rate.

Barthel index for activities of daily living (ADL) at 30 days after surgery.

The ADL score will be analyzed using a linear mixed model, with a random intercept for participant centers and adjusting for planned surgical procedure complexity grade, ASA grade, age, gender, baseline hemoglobin, and baseline creatinine. For any computation complexities, variable transformations or dimension reduction methods will be used.

Clavien-Dindo Grade IV - V complications within 30 days of surgery

Clavien-Dindo Grade IV - V complications within 30 days of surgery will be analyzed using a logistic regression model, adjusting for planned surgical procedure complexity grade, ASA grade, baseline hemoglobin, and baseline creatinine.

The expected event rate for this endpoint is lower than for other outcomes, thus we reduce the number of covariates that included in the model.

Analysis of Safety outcomes

Safety outcomes will be analyzed using the same method as the analysis of primary endpoints.

Interim analyses and stopping rules

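### Acute kidney injury and the other safety outcomes have, on the natural reading, only an unadjusted analysis, although strong candidate covariates are held; a prespecified adjusted AKI estimate would add a little precision at almost no cost

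*SAP*

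**What the plan says.** *Analysis of Safety outcomes* in the SAP is one sentence: "Safety outcomes will be analyzed using the same method as the analysis of primary endpoints". It covers all six items listed under *Safety Outcomes*, the first of which is "Incidence of acute kidney injury diagnosed by KDIGO criteria".

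*Analysis of the primary endpoints* says that the endpoint "will be analyzed using Chi-squared test as crude analysis". It adds an unadjusted risk ratio, a risk difference and a number needed to treat, with 95% confidence intervals for the first two.

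The covariate-adjusted logistic model comes under a different heading, *Secondary Analyses of the primary endpoint*. Its covariates are planned surgical complexity, ASA grade, gender, age, "baseline hemoglobin, and baseline creatinine, NPO duration" and fluid given in the 12 hours before surgery.

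Creatinine, age, ASA grade and complexity also enter the models for length of stay, ideal recovery and the Barthel index. For Grade IV–V complications, where the SAP expects a lower event rate, it shortens the list to complexity, ASA grade, haemoglobin and creatinine, but still adjusts.

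**The concern.** AKI is the first-listed safety outcome of a trial that compares a starch with a crystalloid. Baseline creatinine, age, ASA grade and planned complexity are plausible predictors of it. All four are measured before treatment and are already used in other models of the same SAP. Adjusting for baseline variables that predict the outcome raises the power of a randomised comparison. On the natural reading, the safety sentence gives up that gain.

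The SAP's own treatment of neighbouring outcomes makes the omission look unplanned:

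- Hypotension within 20 minutes of induction, a secondary endpoint, gets a logistic model. Intraoperative hypotension, a safety outcome, gets none.
- Grade IV–V complications, which include dialysis, are adjusted for creatinine. KDIGO AKI is not.
- A low event rate was not treated as a reason to drop adjustment for Grade IV–V.

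At stake is some precision on the AKI comparison, and certainty before unblinding about which AKI analysis was planned.

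**Working it through.** **1. Which method does the safety sentence point to?**

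| SAP section | What it contains | Bearing on the safety sentence |
|---|---|---|
| *Analysis of the primary endpoints* | Crude chi-squared test, unadjusted risk ratio and risk difference | Its title nearly matches the cross-reference |
| *Secondary Analyses of the primary endpoint* | Adjusted logistic model, mixed model, win ratio | Not named |
| *Analyses of exploratory outcomes*, composite components | Similar reference to the primary analysis, then spelled out as unadjusted | Supports the crude reading |
| *Subgroup analyses* | Describes a logistic model as the one used for the primary endpoint | Leaves some doubt |

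The crude reading is the natural one, but it is not certain.

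**2. Evaluable sample size.** The SAP gives 33% v 26%, 90% power, 5% type I error, 10% drop-out and 2020 patients, and it reports two-sided P values. With the pooled two-proportion formula and p̄ = 0.295:

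n = [1.96·√(2·0.295·0.705) + 1.2816·√(0.33·0.67 + 0.26·0.74)]² / 0.07² = 890 per arm

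890/0.9 gives 989 per arm, or 1978 in total (2044 with a continuity correction). The stated 2020 is thus reproduced to within about 3%. Evaluable patients per arm: 1010 × 0.9 = 909. (The 13-point reduction stated beside these rates does not match them, since 33 − 26 = 7. That is a separate matter and does not affect the 909.)

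**3. Crude power for AKI.** The SAP gives no AKI rate, so the rates below are assumptions.

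z = [√n·|p₁ − p₀| − 1.96·√(2p̄(1 − p̄))] / √(p₀(1 − p₀) + p₁(1 − p₁))

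For 5% v 7.5%, p̄ = 0.0625: z = (30.15 × 0.025 − 1.96 × 0.3423) / 0.3419 = (0.7537 − 0.6709) / 0.3419 = 0.242, so power is 0.60. In the same way: 2% v 3% gives 0.28, 2% v 4% gives 0.71, and 10% v 15% gives 0.90.

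**4. Crude against adjusted, by simulation.** There were 909 patients per arm and 2,500 simulated trials per cell. One standard-normal baseline score had a log-odds slope of 0.5, 1.0 or 1.5, giving a c-statistic of about 0.64, 0.75 or 0.84. The chi-squared test was compared with the likelihood-ratio test for treatment in a logistic model containing the score.

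| Assumed AKI rates | c ≈ 0.64 | c ≈ 0.75 | c ≈ 0.84 |
|---|---|---|---|
| 2% v 4% | 0.72 → 0.73 | 0.71 → 0.73 | 0.72 → 0.76 |
| 3% v 4.5% | 0.40 → 0.40 | 0.40 → 0.42 | 0.39 → 0.44 |
| 5% v 7.5% | 0.60 → 0.61 | 0.59 → 0.61 | 0.59 → 0.67 |
| 10% v 15% | 0.90 → 0.91 | 0.91 → 0.93 | 0.90 → 0.95 |

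The gains are about 0–1, 2–3 and 4–8 points for weak, moderate and strong predictors. With ten covariates, nine of them noise, they are similar (5% v 7.5%: 0.60 → 0.60, 0.59 → 0.61, 0.60 → 0.67). With no treatment effect, the adjusted test rejected in 4.4% to 6.0% of trials, close to the crude test.

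**5. A common safety outcome.** At an assumed 30% v 36.5%, with a score SD of 0.7 to 1.4 on the log-odds scale, power rises from 83–84% crude to 88–92% adjusted.

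**The case against.** The best defence is that nothing here is wrong. Randomisation makes the crude comparison valid. The SAP calls everything beyond its single primary analysis exploratory, and it claims no power for safety outcomes. The plan also gives more than a P value, because unadjusted risk ratios and risk differences come with the test. All of this stands, and it limits the point to efficiency.

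A reader might infer that benefit gets the sensitive analysis and harm the insensitive one. The SAP does not support that. The main test of the primary endpoint is crude too. Composite components, mortality, unplanned ICU admission, reoperation and in-hospital complications are also unadjusted. The Grade IV–V model adjusts serious harm, including dialysis, for creatinine.

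The cross-reference can also be read to include the adjusted secondary analysis, given the wording under *Subgroup analyses*. That weakens any claim that adjustment is ruled out, but it is a further reason to settle the wording before unblinding.

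The gain may sit at the low end of the range. Entry excludes eGFR below 30, which narrows the range of creatinine and probably its predictive strength. The unknown AKI rate and size of harm also move power far more than adjustment does. Both remarks stand. Finally, nothing in the SAP suggests that creatinine predicts bleeding, arrhythmia or airway pressure, so the argument is strongest for AKI.

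One might also object that a test of the conditional odds ratio was simulated while a standardised risk difference is recommended. Simulation of the standardised risk difference at 909 per arm shows that it gains as much as the Wald test of the odds ratio.

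**Conclusion.** The point holds as a minor improvement. On its natural reading the SAP plans no adjusted estimate for AKI, although it holds the covariates and uses them elsewhere, even for an outcome that it expects to be infrequent. Adjustment would add about 0 to 8 points of power for AKI at 909 per arm. It could add more for a common outcome with a strong baseline predictor. These figures assume AKI rates of 2% to 10% in the control arm, risk ratios of 1.5 to 2.0 and c-statistics of about 0.64 to 0.84, none of which the SAP gives. They also assume a correctly specified model.

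It should not be inferred that the crude analysis is biased, or that adjustment would rescue an underpowered AKI comparison. At 3% v 4.5%, power stays below 45% either way.

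**What to change.** In *Analysis of Safety outcomes*:

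- Keep the crude table, with its unadjusted risk ratio and risk difference, for all six outcomes, and say that this is what the cross-reference means.
- For AKI, add a logistic model with treatment, baseline creatinine, age, ASA grade and planned surgical complexity. Report a standardised risk difference and risk ratio with 95% confidence intervals.
- For any common safety outcome with a strong baseline predictor already held, do the same with that predictor, for example baseline SBP for the blood-pressure episodes. Name these outcomes before unblinding.
- Leave rare outcomes unadjusted.

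One detail needs care. *Handling of Missing Data* combines imputed results on the log-odds scale. The standardised estimates should be computed within each imputed data set and then combined.

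The cost is a few lines in the SAP and one extra model per outcome concerned. No new data, sample size change or change to the primary analysis is needed.

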Patients who were given intravenous crystalloid boluses before the induction of general anaesthesia did not significantly impact haemodynamic instability [7].

Yet, there are very limited studies and no clear evidence regarding whether preoperative fluid infusion therapy can improve the postoperative prognosis of patients undergoing general anaesthesia. Considering the benefits achieved through preoperative infusion in relation to post-induction hypotension, we thus hypothesize that preoperative fluid infusion can have an impact on

postoperative complications. Additionally, whether the reduction in post-induction hypotension acts as a mediating effect will also be explored.

COIN (Colloid infusion for Optimal outcomes In Non-cardiac surgery(COIN): a randomized controlled trial. Rationale and Design) aims to investigate whether the preoperative colloid infusion before the induction of anesthesia can reduce the postoperative complications of patients planning to undergo non-cardiac surgery with general anaesthesia comparing to crystalloid. The study is a parallel group, blinded, prospective, randomised controlled, multicentre trial with 1 : 1 allocation ratio.

The trial commenced in July 12, 2023 and the estimated timeline for completion of patient accrual was Mar 31, 2025. The participants will be followed until 30 days after surgery. This statistical analysis plan details the pre-planned analyses and statistical considerations for COIN for transparency of data management and analyses procedures. The trial protocol has been submitted to *BMJ Open* (bmjopen-2025-100293).

STUDY OVERVIEW

Ethics and Study Design

The planned study is a parallel group, blinded, randomised, controlled, multi-centre trial conducted at seven tertiary teaching hospitals across China. The study protocol was initially approved by the institutional review board (IRB)

of the coordinating site (Xijing Hospital: KY20232058-F1) followed by institutional IRB approvals from all participating centres. The informed consent will be obtained from patients before enrollment. One interim analysis was planned at 50% information rate (50% enrolled participants) with primary endpoints at 30 days after surgery) with futility stopping rule.

Study Population

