The data safety monitoring board (DSMB) will review the outcome data, safety data and recruitment data during the trial. The DSMB will recommend that the trial to stop early if:

1. There is overwhelming external evidence to convince a broad range of clinicians that one trial arm is clearly indicated or contraindicated, and this new evidence would influence patient management.
2. It becomes evident no clear outcome will be obtained.

In addition, one prespecified interim analysis for futility will be conducted at halfway point of the trial, aka after enrollment of 1010 participant with 30-day follow-up visit for the primary endpoint. The stopping boundary for futility was designed based on O'Brien-Fleming spending function and the decisions will be made by an independent Data and Safety Monitoring Board (DSMB). The defined futility stopping conditions are either $z\text{-score} > 0.263$ or if one-sided $p\text{-value} > 0.3962$. No early efficacy stop was planned for this study as we do not intend to prematurely halt the study based on the observation of early positive results.

The DSMB will also formally evaluate the safety of the trial. The safety outcomes in each group will be reviewed by the DSMB. If the *P*-value for the difference between study groups in any of the safety outcomes is 0.05 or less using a Mann-Whitney rank-sum test and is concordant in direction with the point estimate for mortality, it is recommended that the study be stopped early for safety. Additionally, the DSMB will reserve the right to stop the trial at any point.

No adjustments to the primary analysis and the sample size will be made to account for any interim analysis performed for the DSMB. All unblinded analysis for the DSMB will be performed by an independent statistician not involved in the trial, so as to maintain blinding.

Subgroup analyses

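### The z and p conditions of the futility rule contradict each other; on the scale where the two numbers match, the z inequality is reversed and would stop a succeeding trial

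*SAP*

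**What the plan says.** Under Ethics and Study Design the SAP states: "One interim analysis was planned at 50% information rate", with a futility rule. The section Interim analyses and stopping rules repeats that "one prespecified interim analysis for futility will be conducted at halfway point of the trial", after 1010 participants have 30-day primary outcome data. It adds: "The stopping boundary for futility was designed based on O'Brien-Fleming spending function". The rule itself reads: "The defined futility stopping conditions are either $z\text{-score} > 0.263$ or if one-sided $p\text{-value} > 0.3962". Early stopping for benefit is ruled out: "No early efficacy stop was planned for this study as we do not intend to prematurely halt the study".

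The SAP does not say whether a positive or a negative z favours colloid, or which direction the one-sided p-value tests. It also does not say whether the boundary is binding. The section does state that the primary analysis is not adjusted for the interim look.

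**The concern.** A futility boundary stops the trial when the evidence for benefit is too weak, so a z threshold and a one-sided p threshold for the same boundary must point in opposite directions: low z goes with high p. Here both are written as greater than. Either the z inequality is reversed or the z threshold has the wrong sign, and the reader cannot tell which because the sign of z is undefined.

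This is the only formal statistical boundary for the primary endpoint. If the independent statistician computes z so that positive values favour colloid and the DSMB applies the z condition as printed, the trial stops for futility exactly when colloid looks better. With the opposite sign, the z condition used alone is a weaker futility rule than the one designed.

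**Working it through.** **Inputs.** All are from the SAP.
- Boundary: z 0.263, one-sided p 0.3962, O'Brien-Fleming spending, information fraction t = 0.5, no efficacy stop (Interim analyses and stopping rules).
- Overall type I error 5%, power 90%, event rates 33% and 26%, 1010 per arm including 10% drop-out (Sample Sizes).
- Results reported with "A two-sided P value" (General analysis Principles), so alpha is taken as 0.025 in the benefit direction, with beta = 0.10.

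**Step 1: are the two numbers one point?** 1 − Φ(0.263) = 0.3963, and p = 0.3962 corresponds to z = 0.2632. They are the same point on a scale where larger z gives smaller p.

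**Step 2: reproduce the boundary.**
- Beta spent at t = 0.5: 2 × [1 − Φ(1.645/√0.5)] = 0.0200.
- Solving for total beta 0.10 with the final critical value left at 1.96 (non-binding) gives a drift of 3.276.
- Interim mean: 3.276 × √0.5 = 2.317.
- Lower bound: 2.317 + Φ⁻¹(0.0200) = 2.317 − 2.054 = 0.263 (0.2632 before rounding).

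This matches the SAP. A binding version gives 0.2540, which does not. So 0.263 is a lower bound with positive z meaning benefit.

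The sample size points to the same design. The pooled two-sided formula for 33% versus 26% gives 889.9 per arm; × 1.0217 (the inflation for this design) = 909.1; ÷ 0.9 = 1010. This is corroboration only, because the SAP also says the sample size is not adjusted for the interim analysis.

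**Step 3: test both sign conventions.**
- Positive z favours colloid, p = 1 − Φ(z): p > 0.3962 is z < 0.2632. The printed z > 0.263 is the opposite region, and the two joined by *or* cover the whole line.
- Negative z favours colloid, p = Φ(z): p > 0.3962 is z > −0.263, while z > 0.263 is p > 0.6037. These are two different thresholds.

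No convention makes the conditions agree.

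**Step 4: operating characteristics.** Expected interim z = 0.07/√(2 × 0.295 × 0.705/n), where n is the number per arm. With n = 909/2 = 454.5 this is 2.31; with n = 505 (1010 participants, all with outcome data) it is 2.44. Stop probabilities are normal tail areas around these means, or around 0 under no effect.

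| Scale and condition | No effect | 33% vs 26%, n = 454.5 | 33% vs 26%, n = 505 |
|---|---|---|---|
| Positive = benefit: z > 0.263 alone, as printed | 39.6% | 98.0% | 98.5% |
| Positive = benefit: z < 0.263, same as p > 0.3962 | 60.4% | 2.0% | 1.5% |
| Positive = benefit: both printed conditions joined by *or* | 100% | 100% | 100% |
| Negative = benefit: z > 0.263 alone, as printed | 39.6% | 0.5% | 0.3% |
| Negative = benefit: p > 0.3962, same as both joined by *or* | 60.4% | 2.0% | 1.5% |

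**The case against.** Four points can be made for the plan.

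**The sign is undefined, so reversal is not proven.** The endpoint is adverse, and a colloid-minus-crystalloid statistic would make benefit negative. On that scale greater than is the right direction, the error is a dropped minus sign, and a succeeding trial is not stopped. Because the conditions are joined by *or*, the combined rule then reduces to p > 0.3962, which is the designed rule. This stands as a limit on the consequence: the harm of stopping a succeeding trial depends on the sign. The contradiction does not, since the printed z threshold is wrong under either sign. The pairing of +0.263 with 0.3962 and the reproduced lower bound of +0.2632 both point to the positive-benefit scale.

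**The DSMB would see the misprint.** The text labels the conditions as futility conditions and disclaims stopping for early benefit, and the board has statistical support. That makes the worst outcome less likely. It does not supply an executable rule, and the SAP says the final manuscript will strictly follow it.

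**The look may already have taken place.** The SAP is dated 19 January 2025, and accrual was to run from 12 July 2023 to 31 March 2025 (628 days). If accrual was even, which is an assumption, half was reached after 314 days, in May 2024, with 30-day follow-up complete in June 2024. The correction would then set the record straight and would not prevent a wrong stop. It is still needed, together with a statement of the rule actually applied.

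**Non-binding is not stated in the SAP.** It is inferred from the match at 0.2632 (against 0.2540 if binding) and from the statement that the primary analysis is not adjusted. The sponsor should confirm it.

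**Conclusion.** The rule is wrong as written and must be corrected. Its two conditions disagree under either sign of z. On the scale that the SAP's own numbers imply, the z inequality is reversed: applied alone it stops with probability about 98% when the planned effect is true and 40% under no effect, where the intended rule gives about 2% and 60%. Joined by *or* on that scale, the conditions always stop the trial. On the opposite scale the z condition alone stops 40% of no-effect trials against 60% under the p condition, although the combined rule does work as designed.

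The figures assume 33% versus 26%, 1:1 allocation, a normal approximation, and half of 909 evaluable patients per arm at the look. Using 505 per arm only moves the planned-effect figures to 98.5% and 1.5%. The contradiction itself needs none of these assumptions. The boundary value 0.263 is sound; only the way the rule is expressed is at fault.

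**What to change.** Replace the sentence with a single rule on a defined scale, for example:

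> With z defined so that positive values favour colloid (fewer complications), the non-binding futility boundary at 50% information is z < 0.263, equivalently a one-sided p-value above 0.3962 for the alternative that colloid reduces complications.

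Delete the either/or construction and have the sponsor confirm that the bound is non-binding. Send a note to the DSMB and the independent statistician. If the interim look has already been held, record which rule and which sign were used.

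The cost is one sentence in the SAP and one note. The boundary value, the design and the sample size stay as they are.
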